## **12. Data & Safety Monitoring**

The PI and study team will be responsible for data and safety monitoring.

The PI and/or a member of the research team will be available to the patient for any questions or concerns related to the study. Standard quality assurance will be conducted prior to data analysis.

In accordance with federal regulations, the PI will monitor for, review, and promptly report to the IRB, appropriate institutional officials, sponsor, coordinating center and the appropriate regulatory agency head all unanticipated problems involving risks to subjects or others that occur in the course of a subject's participation in a research study (45 CFR 46.103(b)(5)(i) and 21 CFR 56.108(b)(1)), all AE reports will be reported per the UW IRB policies.

## Appendix A. Baseline Pain Assessment

*Note: this baseline assessment sheet will be provided to patients with the study materials so that it would be available for them to review over the phone.*

### Pain Control for Breast Cancer Patients Undergoing Sentinel Lymph Node Biopsy Research Study

#### Patient Baseline Pain Assessment

The following question will be reviewed with you if you decide to enroll in the study. It will be reviewed when a member of the study team calls you to discuss the study. Please save this paper to help with that discussion.

The following faces represent a person who has no pain, or some, or a lot of pain. Indicate the face that shows the pain you are experiencing right now.

©1983 Wong-Baker FACES Foundation. [www.WongBakerFACES.org](http://www.WongBakerFACES.org)  
Wording modified for adult use. Used with permission.

**Pain Control for Breast Cancer Patients Undergoing Sentinel  
Lymph Node Biopsy Research Study**

**Patient Post-Injection Survey**

This survey has questions about what the injection of radioactive tracer was like for you. Your answers will help us learn what is the best method of controlling pain for this procedure.

The following faces represent a person who has no pain, or some, or a lot of pain. Circle the face that shows the pain you experienced with the injection of radioactive tracer:

©1983 Wong-Baker FACES Foundation. [www.WongBakerFACES.org](http://www.WongBakerFACES.org)  
Wording modified for adult use. Used with permission.

Study ID \_\_\_\_\_

Please fill out the following items about the pain you experienced with the injection of radioactive tracer. All questions about "pain" are asking ONLY about the the pain you experienced in the breast with the injection and not other pain. Please answer questions about the pain you experienced in the breast DURING the injection, not other pain you may be feeling when you are filling out this form.

Check the column to indicate the level of your pain for each word, or leave blank if it does not apply to you. \_\_\_\_\_

	Mild	Moderate	Severe
1 Throbbing	_____	_____	_____
2 Shooting	_____	_____	_____
3 Stabbing	_____	_____	_____
4 Sharp	_____	_____	_____
5 Cramping	_____	_____	_____
6 Gnawing	_____	_____	_____
7 Hot-burning	_____	_____	_____
8 Aching	_____	_____	_____
9 Heavy	_____	_____	_____
10 Tender	_____	_____	_____
11 Splitting	_____	_____	_____
12 Tiring-Exhausting	_____	_____	_____
13 Sickening	_____	_____	_____
14 Fearful	_____	_____	_____
15 Cruel-Punishing	_____	_____	_____

Indicate on this line how bad your pain is—at the left end of line means no pain at all, at right end means worst pain possible.

No Pain	_____	Worst Possible Pain
---------	-------	---------------------

Study ID \_\_\_\_\_

The following are questions about the **pain control** you received for the injection of radioactive tracer. Please mark your answers with check mark(s) or circles.

1) Please mark with check mark(s) which of the following pain treatment(s) you received before your injection of radioactive tracer:

- Lidocaine patch on breast
- Ice on breast
- Vibrating device on breast

If you received a lidocaine patch, was it still on your breast right before your breast was cleaned for the injection of radioactive tracer?

- Yes
- No
- Not Sure
- Did not receive the lidocaine patch

Please answer questions 2-4 by circling the number that matches your level of satisfaction or dissatisfaction with different parts of your care for the injection of radioactive tracer.

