### **5.7 Data Collection:**

#### **5.7.1 Patient-level data collection:**

Patient surveys: Patients will complete one brief pain assessment and one survey during the study period.

Baseline pain assessment: Patients will complete a baseline pain assessment at the time of enrollment using the Wong-Baker FACES pain rating scale (Appendix A). The patients will have been given the Wong-Baker FACES pain rating scale at the time of their initial clinic visit. They will be referred to this scale during the enrollment phone call, and baseline pain score will be recorded.

Post-procedural survey: Patients will also complete a brief survey (<10 minutes) after the radiotracer injection but before initiation of anesthesia (Appendix B). Patients should complete the survey within three hours of receipt of radiotracer injection. This will either occur in the nuclear medicine suite or in the preoperative holding area with an iPad device or paper/pen. This post-procedural survey has intentionally been kept brief to decrease patient burden, which is especially critical as it will be completed on the day of surgery.

Chart review: We will record information including: age, race/ethnicity, medical history of chronic pain or fibromyalgia (yes/no), history of prior breast and axillary procedures (biopsy, surgery), history of prior breast cancer, active narcotic or other pain medication usage (over the past week, use of narcotics including tramadol at least twice weekly and/or daily use of Tylenol, NSAIDs, gabapentin, and/or amitriptyline), breast cancer laterality, tumor histology, grade and size, clinical and pathologic AJCC 8th edition cancer stage, hormone receptor status (estrogen receptor, progesterone receptor, Her2neu), and receipt of neoadjuvant chemotherapy. Additionally, we will record any pain medications taken on the day of surgery prior to the arrival to nuclear medicine (narcotics, Tylenol, NSAIDs, gabapentin, amitriptyline), the time of lidocaine patch application, breast radiology procedure prior to nuclear medicine injection, and sentinel lymph node identification on pathology report. We will also record type of radiotracer received.

**5.7.2 Provider-level data collection:** Nuclear medicine staff surveys: Nuclear medicine technologists will be asked to complete two sets of surveys. Nuclear medicine faculty will be asked to complete the end-of-study survey only.

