## 7. MEASURES

*Primary patient outcome measure:* The Wong-Baker FACES pain rating scale is a standardized 10-point Likert scale that is validated and has utility for patients with lower health literacy (27,28). It has been used in prior studies assessing pain with radiotracer injection for SLN mapping (9–11) (Appendix A).

*Secondary patient survey outcome measures:*

- Short Form McGill questionnaire: This is a validated pain questionnaire taking an average of 2-5 minutes to complete that captures subjective experiences of pain in both sensory and affective categories on a 4-point Likert scale. A total score out of 45 is calculated with sensory and affective sub-scores (29) and has been used in prior studies assessing pain with radiotracer injection for SLN identification (9–11) (Appendix B).
- We will ask questions to determine whether the patient received their intervention as assigned (Appendix B).
- Questions to assess patient experience and satisfaction were drawn from the following:
  - Consumer Assessment of Healthcare Providers and Systems (CAHPS®) questions Surgical Care survey (30) (Appendix B).
  - The American Society of Anesthesiologists Satisfaction with Anesthesia Questions (31) (Appendix B).
  - Studies of patient experience/satisfaction with local analgesia using validated surveys (32–34)(Appendix B)
- Recommendation of topical anesthetic option: We will ask patients whether they would recommend the topical anesthetic option that they received to others (yes/no) and inquire why or why not (open ended)(Appendix B).

*Secondary staff outcome measures:*

- Intervention usability and perceived patient pain:
  - The question to assess intervention usability is adapted from the Single Ease Question developed for assessment of usability after the completion of a task (31). The question addressing perceived patient pain utilizes the Numeric Rating scale (NRS), a validated pain rating scale used previously in provider assessment of patient pain with radiotracer injection (2,32). (Appendix C)
- End of study assessment:
  - The goal of the survey will be to assess experiences with implementing each arm of the study and any identified barriers. Nuclear medicine providers will be asked to rank order the usability and perceived efficacy of the different interventions. Space will be provided for open ended comments on benefits or barriers related to the interventions. (Appendix D)

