## 8. Statistical Considerations

### 8.1 Analysis

Data will be analyzed with intervention arms masked. All scales will be constructed in a manner consistent with scale development, including item non-response. We will compare mean post-procedural pain scores (primary outcome) and other continuous secondary outcomes with ANOVA, testing the null hypothesis that mean post-procedural pain scores will not statistically differ between the control and intervention arms. Pairwise differences between each of the intervention arms and the control arm will be assessed with t-tests. Differences in potential control measures between patients randomized to the control and intervention arms that arise by chance will be examined using a chi-square test or Fisher's exact test for categorical variables and analysis of variance (ANOVA) or Kruskal-Wallis test for continuous variables (depending on distribution), respectively. Should there be significant differences in control measures between arms, an analysis of covariance (ANCOVA) will be used to assess the primary outcome, including significant covariates. Differences in the secondary dichotomous measures (sentinel lymph node mapping, patient recommendation) will be assessed with Chi-Square analysis. We will summarize responses to open ended questions in the patient survey and adherence to intervention. All analyses will follow an intention to treat approach. We will summarize the responses from the nuclear medicine providers/staff to determine what arm was perceived to be the most effective method for pain control and the easiest to administer.

Secondary analysis will be performed on the type of radiotracer received and pain scores.

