### Pain Control for Breast Cancer Patients Undergoing Sentinel Lymph Node Biopsy Research Study

#### Provider Survey for Post-Injection Patients

1) Did the patient arrive with a lidocaine patch on the breast?

[figure not shown]
- Yes
- No but patient in a lidocaine patch treatment arm
- Not applicable- patient NOT in lidocaine patch treatment arm

2) Did the patient require more than one radiocolloid injection?

- Yes
- No

3) Ease of administration:

[figure not shown]
Overall, how difficult or easy was it to administer the intervention? Circle a number on the 7-point rating scale below:

4) Pain score of patient:

This question is interested in your perspective of the patient's pain intensity during the injection. Please do not ask the patient for a numeric pain score for the purposes of answering this question.

Please indicate on the following scale with an X where you think the patient's pain intensity was related to the radiotracer injection.

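### The McGill word grid has no 'none' column, so an overlooked word or a skipped grid scores 0, and the item non-response handling promised in section 8.1 cannot be carried out for it

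*Combined protocol and SAP*

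**What the plan says.** Section 7 lists the Short Form McGill questionnaire as a secondary patient outcome. It says the questionnaire "captures subjective experiences of pain in both sensory and affective categories on a 4-point Likert scale", and adds: "A total score out of 45 is calculated with sensory and affective sub-scores".

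The Patient Post-Injection Survey in Appendix B lists 15 words with three columns: Mild, Moderate and Severe. Its instruction is: "Check the column to indicate the level of your pain for each word, or leave blank if it does not apply to you". A separate pain line follows the grid, and the FACES item comes before it on the same survey.

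On missing items, section 8.1 has one general sentence: "All scales will be constructed in a manner consistent with scale development, including item non-response". It gives no rule specific to the McGill.

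Section 5.7.1 says the survey is completed in the nuclear medicine suite or "in the preoperative holding area with an iPad device or paper/pen". The electronic layout is not described.

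Other questions on the trial's forms do print an option for not applicable. The patch follow-up question offers "Did not receive the lidocaine patch", and the staff survey in Appendix C offers "Not applicable- patient NOT in lidocaine patch treatment arm".

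Section 7 also describes the recommendation item as yes/no, and section 8.1 tests it as a dichotomous measure by chi-square. Question 6 of the survey prints Yes, No and Not Sure.

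**The concern.** A rule for item non-response needs a non-response that can be recognised. On this grid a blank is the valid answer for a word that does not apply, and it is also what an overlooked word or an unanswered grid leaves behind. All three enter the total as 0. The error can only lower a patient's total. At the extreme, a patient who circles a high FACES score and passes over the grid is recorded as 0 out of 45.

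If skipping is equally common in all arms, it shrinks real differences rather than creating false ones. At stake is the sensitivity of a listed secondary outcome, together with a stated commitment on missing items that the form does not allow the analyst to keep.

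**Working it through.** **Inputs.** From the documents: 15 words, three printed columns, a 4-point scale, a maximum of 45, and 40 patients per arm. Assumed, because the documents give none: skipping rates, score distributions, correlation between words, and the size of the McGill effect.

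**1. The stated maximum.** With Mild = 1, Moderate = 2, Severe = 3 and blank = 0, the maximum is 15 × 3 = 45, which reproduces section 7. Blank = 0 is inferred rather than written out, but it is the reading that gives both four levels and 45. One overlooked word costs at most 3/45 = 6.7% of the scale. A skipped grid costs the patient's whole total.

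**2. Scattered words.** Let each word be set to 0 with probability p, equally in all arms. Let V be the variance of the true total and Q the sum over words of the mean squared score.
- The raw difference is multiplied by (1 − p).
- The variance becomes (1 − p)²V + p(1 − p)Q.
- The standardised difference is therefore multiplied by 1/√(1 + [p/(1 − p)] × Q/V).

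A simulation used 15 words scored 0–3 from a latent normal with common correlation ρ, and an arm shift of 0.3 latent SD. At p = 0.10 the percentage fall in the standardised difference was as follows, by control-arm shares scoring 0/1/2/3:

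| ρ | 70/15/10/5 | 50/20/18/12 | 25/25/25/25 |
|---|---|---|---|
| 0 | 6.3 | 7.9 | 11.6 |
| 0.3 | 1.8 | 2.1 | 2.8 |
| 0.5 | 1.2 | 1.3 | 2.0 |
| 0.7 | 0.8 | 1.2 | 1.3 |

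For ρ from 0.3 to 0.7, the fall is 0.4–1.5% at p = 0.05 and 0.2–0.5% at p = 0.02.

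The SD usually falls along with the raw difference, but not always. It rises when Q/V exceeds (2 − p)/(1 − p), which is 1.9/0.9 = 2.11 at p = 0.10. With independent words and equal shares, the control arm has Q/V = 3.5/1.25 = 2.8. The SD then rises, and the standardised difference falls by more than the 10% raw loss.

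**3. Whole grids.** Let a share w of patients skip the grid and score 0. Let r be the mean total divided by its SD.
- The raw difference is multiplied by (1 − w).
- The variance becomes (1 − w)V(1 + w r²).
- The standardised difference is multiplied by √[(1 − w)/(1 + w r²)].

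At w = 0.10:
- r = 0.8: √(0.9/1.064) = 0.920, a fall of 8%.
- r = 1.25 (assumed mean 10, SD 8): √(0.9/1.156) = 0.882, a fall of 12%.
- r = 2.5 (assumed mean 20, SD 8): √(0.9/1.625) = 0.744, a fall of 26%.
- r = 2.6: √(0.9/1.676) = 0.733, a fall of 27%.

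The range of about 8–27% thus corresponds to r between 0.8 and 2.6. The latent model in step 2 with ρ from 0.3 to 0.7 has r of about 0.7 to 2.2, and falls of about 7–22%; weaker correlation pushes the figure up. At lower rates, for r from 0.8 to 2.6, the fall is about 4–16% at w = 0.05 (√(0.95/1.032) to √(0.95/1.338)) and 2–7% at w = 0.02 (√(0.98/1.0128) to √(0.98/1.1352)).

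**4. Effect on a pairwise test.** Take an assumed standardised difference of 0.65, 40 per arm, two-sided 0.05. The normal approximation to power is Φ(0.65 × f × √20 − 1.96), where f is the multiplier.
- No skipping: Φ(0.947) = 83% (82% by the t-test).
- Scattered, falls of 1% and 3%: Φ(0.918) = 82% and Φ(0.860) = 81% (rounded).
- Whole grid, falls of 8% and 27%: Φ(0.714) = 76% and Φ(0.162) = 56%.

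The protocol does not power this outcome, so these figures are illustrations only.

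**5. Recommendation item (minor note).** Two constructed tables of 40 per arm, as Yes/No/Not Sure:
- 20/14/6, 26/8/6, 24/6/10, 30/4/6: p = 0.136 for Yes against the rest, 0.037 with Not Sure excluded, 0.095 with three levels.
- 18/10/12, 25/8/7, 27/9/4, 30/8/2: p = 0.040, 0.587 and 0.051 in the same order.

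These tables were built to show that the handling can matter in either direction. They do not show that it is likely to.

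**The case against.** The strongest reply is that the form and section 7 agree. Blank plus three marked levels is a 4-point scale with a maximum of 45, and the instruction tells the patient what a blank means. That stands. A reader might infer that Appendix B contradicts section 7, but the documents do not support this. The conflict is with the non-response sentence in section 8.1, which needs information the grid does not collect.

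A reader might also infer that the McGill comparison is biased towards one arm. Nothing in the documents suggests that skipping depends on arm, and equal skipping dilutes differences. The opposite inference, that the effect is always negligible because the SD shrinks too, also fails: step 2 has a case where the SD rises, and whole-grid skipping costs far more than scattered words.

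Other points carry some weight. The patch and staff questions are single items about treatment received, so they are only loose comparators for 15 pain words. The iPad version is not shown and may already separate the two meanings. The survey was deliberately kept short.

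On the recommendation item, masking of arms under section 8.1 limits steering towards a favoured arm. The second constructed table needs Not Sure at 12/40 = 30% in one arm and 2/40 = 5% in another. Intention to treat concerns analysis by assigned arm and does not settle what Not Sure means.

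**Conclusion.** The point holds as a low-severity improvement to a secondary outcome. On this form a blank cannot be classified as an answer or a non-response, so section 8.1's commitment cannot be met for the McGill words.

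If 10% of words are skipped at random in every arm, the standardised difference falls by about 1–3% with correlated words, and by about 6–12% with independent words. If 10% of patients skip the whole grid, it falls by about 8–27%. Every rate and distribution behind these figures is assumed; actual skipping may be much rarer. The primary FACES outcome, the stated power and the sample size are unaffected.

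The Not Sure mismatch is real, but it is a minor matter of wording and an unwritten coding rule.

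**What to change.** Add a 'None (0)' column to the 15-word grid and ask for one mark per word, on paper and iPad. A blank then means missing. Record the form version for each patient.

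For forms already completed, keep blank = 0 for single words, since nothing on the form can separate the meanings. Treat an all-blank grid as missing when the FACES item or the pain line on the same survey shows pain; otherwise score it 0. Report all-zero scoring as a sensitivity analysis, because a patient can have pain that none of the 15 words describes. Write this into section 8.1 before the responses are examined.

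The costs are a changed layout in a questionnaire that section 7 calls validated, more marks on a brief survey, and two pooled form versions. With all four arms randomised over the same period, versions should be roughly balanced across arms. Forms completed earlier keep the single-word ambiguity.

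Separately, correct section 7 to show three response options for question 6, and state one handling in section 8.1 before responses are examined. Yes against No or Not Sure, or a three-level chi-square, would each do. Intention to treat should not be given as the reason. This costs two sentences. Counting Not Sure with No gives a lower recommendation rate than excluding it.

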**How satisfied are you with:**

	Very Satisfied	Satisfied	Somewhat Satisfied	Somewhat Dissatisfied	Dissatisfied	Very Dissatisfied
2) how the staff paid attention to your complaints like discomfort or pain with the injection?	1	2	3	4	5	6
3) the care provided by the staff performing your injection?	1	2	3	4	5	6
4) the pain control you received for the injection?	1	2	3	4	5	6

**Study ID** \_\_\_\_\_

5) Please circle the answer that matches your anxiety during the injection:

Very Anxious	Moderately Anxious	Slightly anxious	Not at all anxious
1	2	3	4

6) Please mark your answer to the following statement with a check mark.

I would recommend the pain control I received to others undergoing the same procedure.

- Yes
- No
- Not Sure

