### 3.4 Preliminary observations

*Options for topical anesthetic:* Institutionally and in the literature, EMLA cream does not appear to reduce pain with radiotracer injection (13–15). The nuclear medicine department at our institution discontinued the use of EMLA due to perceived lack of efficacy and workflow challenges associated with implementing EMLA application into practice (which may have impacted effectiveness).

The current standard of care at our institution is application of ice to the breast before radiotracer injection. Application of ice to the breast has not been directly studied in the setting of radiotracer injection, but ice and topical vapocoolant sprays have been found to reduce the pain of procedures such as venous and arterial cannulation in adults (17–20). According to breast cancer providers at our institution, patients continue to report significant pain with the procedure when ice is used as the topical anesthetic.

Lidocaine patches, in contrast to EMLA, are easier for patients and providers to apply and have demonstrated efficacy in neuropathic pain as well in aesthetic procedures (21–23). This represents a potential option for a topical anesthetic.

*Novel intervention for procedural pain:* Topical high frequency vibration combined with topical cooling is a novel method to alleviate acute procedural pain. It has been studied and implemented largely in the pediatric population. It is thought that mechanoreceptor and noxious thermal inhibitory stimulation alter normal pain conduction pathways and offers better pain control than cooling alone (24). This combined approach has been found to significantly reduce the pain and distress of venipuncture (25). This intervention is the most commonly used non-pharmacologic intervention for venipuncture pain within our institution's Children's Hospital with good anecdotal success in reducing pediatric pain. The literature in the adult population of combined vibration and cold therapy is much scarcer, but preliminary data suggests that this intervention is beneficial especially in those with greater pre-procedural anxiety and is superior to cooling alone (24). A combination of vibration and cooling has not been widely implemented in our adult population for any acute procedural pain, making it an underexplored and promising area of study. Our initial observations are that application of this type of vibration to the periareolar breast and even nipple areolar complex is tolerable.

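### Improvement, not an error: anxiety is recorded only after treatment, so there is no pre-treatment value for adjustment or for an exploratory look at the modifier the background cites

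*Combined protocol and SAP*

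**What the plan says.** In section 3.4 the adult evidence for combined vibration and cold is summarised in one sentence: "preliminary data suggests that this intervention is beneficial especially in those with greater pre-procedural anxiety and is superior to cooling alone". Section 5.7.1 limits patient-reported data to two occasions: "Patients will complete one brief pain assessment and one survey during the study period". The first is at enrolment: "Patients will complete a baseline pain assessment at the time of enrollment using the Wong-Baker FACES pain rating scale". The Appendix A form carries a single item: "Indicate the face that shows the pain you are experiencing right now". The second is the survey completed "after the radiotracer injection but before initiation of anesthesia", within three hours of the injection. Its question 5 is the only anxiety item: "Please circle the answer that matches your anxiety during the injection", on four levels.

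Anxiety appears nowhere else as a planned measurement. It is not among the chart-review items in 5.7.1 (which include "medical history of chronic pain or fibromyalgia (yes/no), history of prior breast and axillary procedures (biopsy, surgery), history of prior breast cancer"), the stratification factor in 5.5, the schedule of events in 5.8, the measures in section 7 or the analysis in 8.1. The McGill descriptor for fear is collected in the same post-injection survey and describes the injection pain.

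Section 8.1 compares mean FACES scores by ANOVA. It moves to ANCOVA only if control measures, which it does not list, differ significantly between arms.

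**The concern.** The background singles out patients who are anxious before the procedure as those likely to gain most from the device, yet that state is never recorded. Question 5 asks about a different moment. By then the intervention has been given, and in arms B and D the device is still on the breast. The answer can be influenced by the arm and by the pain itself, so it cannot stand in for a baseline value, and subgroups formed on it are not protected by randomisation.

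Two things are at stake, both secondary. Anxiety before an injection is a plausible predictor of the pain score, so a baseline value could sharpen the adjusted comparison. It would also allow a first look at whether the device's benefit varies as section 3.4 suggests. Neither can be recovered once a patient has been treated.

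**Working it through.** **Inputs from section 8.2:** control mean 6.0; SD 2.6 in every arm; 2-point difference between control and the best arm; 40 per arm; alpha 0.05; stated power 85%. The two middle means are not given. The documents give no anxiety-pain correlation r, so r is an assumption, shown over a range.

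**1. The plan's own figure.** For a one-way ANOVA the noncentrality is λ = n × Σ(mean − grand mean)² / SD², on 3 and 156 degrees of freedom. With evenly spaced means 6, 5.33, 4.67, 4 the sum of squares is 1 + 0.111 + 0.111 + 1 = 2.222. Then λ = 40 × 2.222 / 6.76 = 13.15 and power is 86.6%. Means of 6, 5, 5, 4 give 82.4%. The stated 85% lies between these, so it is reproduced to within the unstated middle means.

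**2. Gain from a baseline covariate.** Residual variance becomes 6.76 × (1 − r²), and the equivalent unadjusted sample size is 160 / (1 − r²).

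| Assumed r | Residual SD | λ | Power, evenly spaced means | Equivalent N |
|---|---|---|---|---|
| 0 | 2.60 | 13.15 | 86.6% | 160 |
| 0.1 | 2.59 | 13.28 | 86.9% | 162 |
| 0.2 | 2.55 | 13.70 | 88.0% | 167 |
| 0.3 | 2.48 | 14.45 | 89.8% | 176 |
| 0.4 | 2.38 | 15.65 | 92.2% | 190 |

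Losing one degree of freedom to the covariate does not change these at the precision shown. They compare adjustment for anxiety with no adjustment at all; overlap with other baseline covariates would reduce the gain.

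**3. What an interaction test could show.** Take B+D against A+C, 160 patients, half of them high-anxiety (assumed), so 40 per cell. SE = 2.6 × √(4/40) = 0.82. Two-sided power at 0.05 is about Φ(d/SE − 1.96): 23% for an interaction of 1 point, 68% for 2 and 95% for 3. The interaction detectable with 80% power is (1.96 + 0.84) × 0.82 = 2.3 points. With A against B only (20 per cell), SE = 2.6 × √(4/20) = 1.16, power is 14% and 41% for 1 and 2 points, and the detectable interaction is 3.3 points.

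**4. Why question 5 is not a substitute.** Suppose the true effect is −2 points, treatment lowers anxiety by a SDs, and each SD of anxiety adds b pain points. Adjusting for question 5 then gives −2 + a × b. With assumed a of 0.2 to 0.5 and b of 0.5 to 1.5, the adjusted effect runs from −2 + 0.10 = −1.90 to −2 + 0.75 = −1.25. This only illustrates the risk; the plan does not propose that adjustment.

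**The case against.** The strongest reply is that the plan never gives anxiety either role. The objectives are pain, satisfaction and barriers to implementation, and 8.1 contains no anxiety adjustment, subgroup or interaction. The remark in section 3.4 is a hedged half-sentence in a paragraph that also rests on mechanism, venipuncture results and tolerability. This stands, and it is why the point is an improvement and not an error.

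A reader might infer that the primary comparison is biased, or that the plan contradicts its own rationale. The documents support neither: allocation is randomised and no test of modification is promised. A reader might also infer that question 5 is going to be used as a covariate. Section 8.1 ties its balance checks to chance differences between arms, which does not naturally describe a response that treatment can alter. Because the control measures are not listed, one clarifying sentence is still useful.

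It also stands that the correlation is assumed and the precision gain modest, that anxiety at enrolment may differ from anxiety on the day of injection, and that the interaction test is weak: 2 points is the whole difference section 8.2 treats as clinically significant. What the objection does not remove is that the item costs almost nothing and cannot be collected afterwards.

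**Conclusion.** The point holds as a low-cost improvement. The trial records anxiety only after treatment and so has no valid baseline value for it. The primary randomised comparison and the stated power do not depend on one. With evenly spaced means and an assumed correlation of 0.1 to 0.4, adjustment would add roughly 0.3 to 5.6 percentage points of power (86.6% to between 86.9% and 92.2%), less if anxiety overlaps with other covariates. The modifier question could be explored but not settled with 160 patients.

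**What to change.** - **Appendix A and section 5.7.1:** add one 4-point item on anxiety about the coming injection to the baseline assessment. Ask it at enrolment, by phone or in person, after consent and before randomisation, and state that order.
- **Section 8.1, covariate:** name the item as a baseline covariate in an adjusted FACES model that is fitted whether or not the arms look imbalanced. This departs from the present rule of adjusting only after a significant difference, so that sentence needs rewording.
- **Section 8.1, interaction:** report one vibration-by-baseline-anxiety interaction (B+D against A+C), labelled exploratory. Note that arm C has no ice while arm D does, so this contrast is not vibration alone in the lidocaine pair.
- **Question 5:** state that it is an outcome only and never a covariate or subgroup variable.

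The cost is a few seconds per patient, a form revision and a short edit to 8.1. The limits are that enrolment anxiety is only a proxy for anxiety on the day and that the interaction estimate will be imprecise.
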